a structured simplified scoring guide (contained on the record form) yields a maximum score of 20. There is an additional detailed scoring guideline and associated transparency available as of 2008 to improve inter-rater reliability in scoring this subtest (this is the only subtest for which scoring is not entirely objective).

Line Orientation: Subjects are shown an array of 13 lines, fanning out from a common point of origin through 180 degrees. For each item, two target lines are shown beneath the array, and subjects must identify which lines they match within the array. There are 10 items, each containing two lines to be matched, for a total maximum score of 20.

Language

Picture Naming: This is a confrontation naming task, with 10 line drawings of objects that must be named by the subject.

Semantic Fluency: Subjects are given 60" to provide as many exemplars as they can from a given semantic category (e.g., fruits and vegetables).

Attention

Digit Span: This is a classic digit repetition test of working memory, with stimulus items increasing in length from 2 digits to 9 digits. Items are administered in order of length, and the test is discontinued after failure of two items at a given string length.

Coding: This processing speed subtest is very similar to the Digit Symbol subtest of the Wechsler scales. Subjects must fill in digits corresponding to shapes as quickly as they can on the basis of a coding key. After completing practice items, subjects have 90" to complete as many items as they can.

Delayed Memory

List Learning Free Recall: Free recall of the words from the initial List Learning subtest (max=10).

List Learning Recognition: Yes/No recognition for the words from List Learning, with 10 foils (max=20).

Story Memory Free Recall: Free recall of the story from the Story Memory subtest (max=12).

Figure Free Recall: Free recall of the Figure from the Figure Copy subtest (max=20).

Scoring: The raw scores from the subtests are scaled together to create index scores, and these are summed for conversion to a total scale score. The scaling tables are contained in the stimulus booklets, and computation of index scores requires less than 5 minutes.

Risks: There are no known risks for administering the RBANS.

Justification: The RBANS is simple to administer and is done so by trained personnel. The RBANS has been clinically validated and is a standard tool for assessing changes in cognition in clinical trials of schizophrenia (99). Study personnel have experience administering the RBANS, and it has been recently used in a published phase II clinical trial in schizophrenia by members of the study team (81).

Drug

The drug to be used in this study is (S)- α -ethyl-2-oxo-pyrrolidine acetamide (Levetiracetam, also known as Keppra). This drug is structurally similar to Piracetam, a synthetic derivative of the inhibitory neurotransmitter GABA. It can be administered orally and is typically prescribed for the management of seizures in doses from 500-1500 mg (31).

Risks: LEV is generally well tolerated at the lowest clinically-used of 3,000 mg/day. As such, using ultra-low dose of 125 mg BID is expected to be extremely well tolerated. The most common side effects are drowsiness, asthenia, and dizziness. More rare side effects are insomnia, anorexia, rhinitis, depression, nervousness, mood swings, ataxia, vertigo, amnesia anxiety, and hostility. LEV has no known drug interactions. Side effects will be monitored during the trial on a weekly basis. Stopping and subject withdrawal criteria are described in Study Design and Research Methods.

E. Potential Scientific Problems:

None.

F. Data Analysis Plan:

RBANS

The RBANS has a total scale score and 5 index scores. The scores are scaled with a mean of 100 and a standard deviation of 15. Comparisons (LEV vs. placebo) will be performed using mixed-effects, repeated measures models.

fMRI

The fMRI data will be preprocessed using fMRIprep (Esteban et al., 2019). Condition effects (LEV vs. placebo) will be analyzed using mixed-effects, repeated measures models. Mean hippocampal BOLD response will be examined using an anatomically defined region of interest.

Clinical Symptoms

Effects of drug on BPRS, C-SSRS, SANS, GAF, and AIMS scores in patients will be evaluated using two-tailed paired t-tests. Effects of drug on total scores (e.g. total SANS, total BPRS) will be considered significant at a threshold of $p < 0.05$. Effects of drug on symptom subscales (e.g. SANS alogia) will be considered significant using a multiple comparisons-corrected threshold.

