Document: Protocol and SAP

Study title: Reducing Hippocampal Hyperactivity and Improving Cognition in Schizophrenia

NCT: 03034356

Document date: 6/12/2023

COMIRB Protocol

COLORADO MULTIPLE INSTITUTIONAL REVIEW BOARD
[name] [contact] [contact]

Project Title: Reducing Hippocampal Hyperactivity and Improving Cognition in Schizophrenia

Principal Investigator: **[name].**

Co-Investigator: **[name].**

I. Hypotheses and Specific Aims:

Schizophrenia is a leading cause of disability for Veterans. Among the symptoms of the illness, cognitive dysfunction remains the least well-treated (1). Consequently, much effort has been devoted to developing novel treatments for cognitive deficits in schizophrenia, using a variety of pharmacologic targets (2-4). Nonetheless, no compound has yet earned a federal indication for improved cognition in schizophrenia.

Using human functional imaging, studies have demonstrated that hyperactivity of the hippocampus may be a fundamental characteristic of schizophrenia. Namely, loss of hippocampal gray matter, as well as increased resting metabolism and neuronal activity are all observed (5-12). Recent work from our lab also has found hippocampal hyperactivity to be associated with poor cognition (12). As such, using hippocampal hyperactivity as a target biomarker may be a useful strategy for therapeutic development.

Two recent studies have found that low doses of the anti-epileptic drug levetiracetam (LEV) reduce hippocampal hyperactivity in patients with mild cognitive impairment (MCI), and that this effect correlates with improved performance on a memory task (13, 14). Unlike other anti-epileptic drugs, LEV also has pro-cognitive effects in patients with epilepsy (15-19), and improves cognition in mouse models of Alzheimer's disease (20, 21). Our lab also has recently shown that low-dose LEV improves hippocampal inhibitory function in a rodent model of schizophrenia (22). Compared to other anti-epileptic drugs, LEV is not significantly (<10%) protein bound upon administration, making it less likely to adversely interact with antipsychotic medication (23). Based on this evidence, the overall goal of this study is to test the hypothesis that LEV reduces hippocampal hyperactivity and improves cognition in schizophrenia.

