Previous studies from our laboratory have demonstrated that hippocampal hyperactivity can be pharmacologically reduced in schizophrenia. The majority of our previous neuroimaging work in schizophrenia has focused on the role of nicotinic agonists on the brain and behavior. We have studied the effects of these drugs in part due to their ability to normalize inhibitory hippocampal

circuity due to deficits in nicotinic receptor expression on inhibitory interneurons (67). Specifically, we have demonstrated that acute administration of nicotine (4 – 6 mg gum) (68) as well as chronic (4 weeks) 150 mg b.i.d. administration of the $\alpha 7$ receptor partial agonist DMXB-A (69) reduces hippocampal hyperactivity in patients during SPEM. More recent work in our lab has demonstrated that nicotine and DMXB-A also reduce hippocampal hyperactivity at rest.

While it could be rightly argued that positive symptoms in schizophrenia have a more established relationship with hippocampal hyperactivity, and are a worthwhile treatment goal, a key motivation for this proposal is our recent discovery of a compelling relationship between hippocampal activity and cognitive symptoms, which, as outlined above, constitute a greater unmet treatment goal. We found a relationship between cognition, as measured by the MCCB, and resting state hippocampal activity, as part of the default network, in a cohort of 27 schizophrenia patients (12). A significant inverse correlation was observed between hippocampal activity and MCCB composite score ($R = -0.53$, $p = 0.004$). This effect was driven by effects on attention/vigilance ($R = -0.41$, $p = 0.031$), working memory ($R = -0.41$, $p = 0.031$) and visual learning ($R = -0.41$, $p = 0.032$). A significant positive correlation was observed with negative symptoms (total SANS score; $R = 0.42$, $p = 0.028$).

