of Alzheimer's disease (AD) (20, 21) and AD patients with epilepsy (80). LEV improves pattern recognition memory in patients with mild cognitive impairment (MCI) (13, 14).

Neurobiologically, low dose LEV reduces hippocampal hyperactivity both in rodent models of AD (20, 21) as well as in patients with MCI (13, 14). Motivated by this finding, we examined LEV effects in the DBA/2 mouse model of schizophrenia. The measure of hippocampal inhibitory function used was P20-N40 event-related potential (ERP) auditory gating, the mouse equivalent of the human P50 auditory gating paradigm, a widely used measure of human inhibitory neuronal function. Deficits in P50 gating (the ability of neuronal circuits to reduce early post-stimulus response to the second of a pair of identical, repeated clicks) are theorized to be due to dysfunction in inhibitory circuitry in the hippocampus, with drug effects on rodent gating being highly predictive of human effects (e.g. as with DMXB-A (81-83)). We found that a low LEV dose was associated with improved inhibitory gating (22). In summary, these preliminary data, along with prior reports of LEV effects on both hippocampal activity in different patient populations as well as its pro-cognitive effects in epilepsy, provide strong preliminary support for the proposal hypothesis.

IV. Research Methods

A. Outcome Measure(s):

Primary Endpoint

- 1) The effects of 4 weeks of LEV vs. placebo treatment on cognitive function (RBANS Total Scale score).

Secondary (Exploratory) Endpoints

- 1) The effects of 4 weeks of LEV vs. placebo on resting hippocampal activity.
- 2) Correlation between the effects of 4 weeks of LEV on cognitive function and the effects of LEV on resting hippocampal activity.
- 3) The effects of LEV vs. placebo on individual cognitive assessment domains (e.g. Attention).
- 4) The effects of LEV vs. placebo on clinical symptoms (BPRS/SANS/GAF/AIMS).
- 5) The effects of LEV vs. placebo on hippocampal CBF, measured by arterial spin labeling (ASL).
- 6) The effects of LEV on hippocampal and selective-attention-related neuronal activity.
- 7) The effects of LEV on hippocampal activity during a memory task (pattern separation).
- 8) Side effects and tolerability.
- 9) Treatment (drug or placebo) X smoking status (smoker or non-smoker) interaction effects.
- 10) The effects of LEV vs. placebo on eating behaviors (TFEQ/FCQ/PFS/VAS) will also be assessed as exploratory aims, given potential LEV effects on appetite (114).

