After the second ~4-week treatment arm has been completed (LEV or placebo, depending on randomized treatment order), participants will complete the Post-Intervention 2 Study Day (“Study Day 3”). This will include the same measures as the Baseline Study Day, described above. Additionally, participants will turn in their completed pill logs, their pill vial, and any remaining pills that were not taken. On the morning of Study Day 3, participants should arrive in a fasted state (not having eaten for approximately 2 hours, same as the baseline day) and take their pill with research staff when they come in for their visit (i.e., they should not take it at home before coming in). The MRI scan will be timed to start approximately one hour after the participant takes their pill.

A table of study procedures is below:

Visit	Cognitive Battery	Primary Neuronal Measure	Clinical Measures	Additional Measures	Compliance	Safety
1: Screening			BPRS; AIMS; C-SSRS	Demographics; test for nicotine use/dependence; smoking history; CO breath test; handedness; weight; hearing test; COVID-19 impact		Written informed consent; physical exam; medical history; MRI screening form; concomitant meds; vital signs;

						urinalysis; blood draw
2: Baseline Study Day	RBANS	fMRI resting state (2 scans)	BPRS; SANS; GAF; AIMS; C-SSRS	fMRI sensory + cognition; anatomical MRI; food- related questionnaires (TFEQ; FCQ; PFS; VAS); weight; subjective improvement; CO breath test; Post MRI questionnaire	Pill pick-up	Physical exam; MRI screening form; concomitant meds; vital signs; urinalysis
3: Check-In			BPRS; C-SSRS	Weight	Pill log, pill count, and pill pick-up	Side effects; vital signs; concomitant meds
4: Study Day 1	RBANS	fMRI resting state	BPRS; SANS; GAF; AIMS; C-SSRS	fMRI sensory + cognition; anatomical MRI; food- related questionnaires (TFEQ; FCQ; PFS; VAS); weight; subjective improvement; CO breath test; Post MRI questionnaire	Pill log, pill count	Side effects; physical exam; MRI screening form; concomitant meds; vital signs; urinalysis
5: Study Day 2	RBANS	fMRI resting state	BPRS; SANS; GAF; AIMS; C-SSRS	fMRI sensory + cognition; anatomical MRI; food- related questionnaires (TFEQ; FCQ; PFS; VAS); weight; subjective improvement; CO breath test; Post MRI questionnaire	Pill pick-up	Side effects; physical exam; MRI screening form; concomitant meds; vital signs; urinalysis
6: Check-In			BPRS; C-SSRS	Weight	Pill log, pill count, and pill pick-up	Side effects; vital signs; concomitant meds

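### Does summarising the fMRI data as mean hippocampal BOLD response leave the resting-activity endpoints without a measure, and is the ASL endpoint left without a scan?

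*Combined protocol and SAP*

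**What the plan says.** Section IV.F covers fMRI in three sentences: preprocessing with a named pipeline, mixed-effects repeated-measures models for levetiracetam (LEV) against placebo, and then "Mean hippocampal BOLD response will be examined using an anatomically defined region of interest". Rest and task are not treated separately.

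The exploratory endpoints in IV.A include both kinds of scan. Endpoint 1 is "The effects of 4 weeks of LEV vs. placebo on resting hippocampal activity". Endpoint 2 is "Correlation between the effects of 4 weeks of LEV on cognitive function and the effects of LEV on resting hippocampal activity". Endpoint 7 is a task measure: "The effects of LEV on hippocampal activity during a memory task (pattern separation". Endpoint 5 is hippocampal blood flow measured by ASL.

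In the visit table of IV.C, the resting scan sits under the column "Primary Neuronal Measure", and the Baseline Study Day entry is "fMRI resting state (2 scans". The Preliminary Studies section reports its link with cognition (R = -0.53) for "resting state hippocampal activity, as part of the default network, in a cohort of 27 schizophrenia patients".

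**The concern.** A response is ordinarily a change relative to a stimulus or condition. A resting run has neither, so the one summary in IV.F seems to have no meaning for endpoints 1 and 2. If it were taken as the average of the signal over time, it would carry no information about resting fluctuations. The measure behind the preliminary correlation, a default-network measure, is not carried into the analysis section. ASL is the only endpoint in blood-flow units, and no scan list mentions it.

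The stakes would be interpretive. The protocol says "the overall goal of this study is to test the hypothesis that LEV reduces hippocampal hyperactivity and improves cognition in schizophrenia", so hippocampal activity is half of the hypothesis. An uninformative summary could give a null result that is misread as a failure to reach the biological target. A metric chosen after the data are seen would raise the false-positive rate.

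**Working it through.** The documents state no figure for the imaging endpoints that could be reproduced, so the check is mainly textual.

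**1. What is being averaged.** There are two possible readings of the IV.F sentence.

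- *Mean over time of the signal.* For a centred series, (1/T) Σ(y_t − ȳ) = 0. For a series scaled to mean 100, LEV minus placebo is 100 − 100 = 0. This reading cannot show any effect.
- *Mean over voxels in the region.* The summary is (1/V) Σ M_v, where M is the map under analysis: a task contrast for a task scan, a resting-activity map for a resting scan. This difference is free to vary with treatment.

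The sentence names an anatomical region and never mentions time, so the second reading is the natural one. What stays open is which resting map M is used. The first reading is an inference from the word response.

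**2. How the protocol uses that word.** The Background section, describing basal blood volume, calls it a response that predicts progression to psychosis. The fMRI justification in IV.D describes the biological target as a lowered hippocampal response, although the main neuronal measure is a resting scan. The authors do not keep the term for stimulus-evoked change.

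**3. Which resting scans enter.** The visit table gives 2 + 1 + 1 + 1 = 5 resting scans.

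| Scan | State | Role implied by the text |
|---|---|---|
| Baseline, first | before any pill | baseline |
| Baseline, second | about one hour after the first pill | acute response, as IV.C states |
| Study Day 1 | after the first ~4-week period | endpoints 1 and 2 |
| Study Day 2 | after washout, no pill | period baseline |
| Study Day 3 | after the second ~4-week period | endpoints 1 and 2 |

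Endpoint 1 specifies four weeks of treatment, which points to Study Days 1 and 3. The imaging term of endpoint 2 omits the duration, but it is correlated with a four-week cognitive effect, so the same visits are implied.

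**4. ASL.** It appears in endpoint 5. It does not appear in the Baseline MRI description (which later study days repeat), the visit table, the procedures in IV.D or the analysis in IV.F. The MRI description says what the scan includes and does not claim to be complete. Either ASL is acquired and hippocampal blood flow goes into the LEV-versus-placebo model that IV.F already prescribes, or it is not acquired and endpoint 5 is not reported. No other endpoint changes in either case.

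**5. False-positive rate from a late choice of metric.** With k independent candidates at 5%, the chance of at least one false positive is 1 − 0.95^k:

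- k = 1: 0.05
- k = 2: 1 − 0.9025 = 0.0975
- k = 3: 1 − 0.857 = 0.143

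Reaching k = 3 means counting the default-network measure, mean BOLD response and ASL blood flow as interchangeable. ASL is a separate listed endpoint. Mean BOLD response taken as a scaled time-mean is constant and could not be picked as a positive result. The documents do not fix the true number of candidate resting metrics, so none of these values is established for this trial. IV.F sets p < 0.05 for total symptom scores but states no threshold for fMRI.

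**The case for a change.** The strongest case for acting is that the exploratory label understates the role of the resting scan. It is the protocol's own main neuronal measure, reduced hyperactivity is half the hypothesis, and IV.D relies on fMRI to show whether the target is reached. One sentence naming the resting summary would close the gap at no cost in scans or visits.

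Part of this stands. The documents do not say how a resting run becomes one value per participant and visit, and a reader of the results may fairly ask when the metric was fixed. ASL is also plainly listed in one place and missing from the others.

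The rest is weaker. A simulation can be built in which the unscaled time-mean has power of about 0.05 against a 20% fall in fluctuation amplitude, while an amplitude summary of the same scans has power of 0.58 to 1.00 with 20 to 40 participants. The first result is built in, because the simulated drug changes only the variance. The sample size, the effect and the variability are all assumed, and the time-mean is an analysis nobody proposed. The obvious replacement, the default-network measure, cannot be computed from these documents because its derivation lies in a cited paper. Preferring it would rest on one correlation in 27 patients. The preliminary drug evidence also includes reduced hippocampal activity during an eye-movement task, which a mean BOLD response fits well.

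**Conclusion.** No change follows. The missing resting metric is a detail that the imaging team must supply before any analysis can run, and the plan's sentence is compatible with a sensible choice. The four-week wording and the stated acute purpose of the second Baseline scan settle which scans enter. The ASL mismatch is a consistency slip affecting one exploratory endpoint.

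Three of the ten exploratory endpoints are thinly described, and the primary RBANS comparison is unaffected. No loss of power and no specific false-positive rate can be attributed to the plan, since both would rest on inputs that the documents do not give. The conclusion assumes that the resting metric is settled before treatment order is unblinded. If it were not, the results for endpoints 1 and 2 would be hypothesis-generating only, which is consistent with the exploratory label they already carry.

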B. Description of Population to be Enrolled

Subjects will be selected to be males and females 18 to 70 years old. We will include people who fulfill DMS-V criteria for schizophrenia or schizoaffective disorder. Participants will be excluded for current substance abuse, severe neurological disorders, head trauma/injury if

expected to affect MRI results, current prescription of LEV or a Non-vitamin K antagonist anticoagulant, if they are capable of pregnancy (i.e. pre-menopausal and not practicing at least one form of birth control), and for fMRI exclusion criteria (e.g., claustrophobia, weight>400lbs, metal in the body). Participants will also be excluded for recent psychiatric instability, as defined by a recent (< 2 months) change in antipsychotic medication and/or a recent (< 3 months) hospitalization for psychiatric symptoms. Both smoking and non-smoking subjects will be included. Subjects will have normal renal function, as assessed by a metabolic panel at screening if results current within one year are not already available. Subjects will be in generally good health as determined by a physical exam (blood pressure, pulse, cardiac, pulmonary, abdominal exam, neurological exam) at the time of screening or based on results from a physical exam within the last 6 months.

C. Study Design and Research Methods

A double-blind crossover design will be used. Participants will complete ~4 weeks of treatment with LEV 125 mg BID and ~4 weeks of treatment with placebo, with a ~4-week washout period between treatment arms. This ultra-low dose is well below the typical clinically used dose of 3,000 mg/day, which is generally well-tolerated. Participants and researchers working directly with them will be blind to treatment order (i.e., LEV/placebo or placebo/LEV). A statistician involved in the study will determine the treatment randomization scheme. Following phone screening, participants will complete an in-person screening day and 4 Study Days (Baseline Study Day, Post-Intervention 1 Study Day, Post-Washout Study Day, Post-Intervention 2 Study Day). They will also complete a Check-In visit ~2 weeks into each 4-week treatment period. Patients with a confirmed diagnosis of schizophrenia or schizoaffective disorder will be targeted for recruitment. If needed, proper diagnosis will be confirmed using the Structured Clinical Interview for DSM-V Axis I Disorders (SCID), administered by trained personnel (study staff or a member of the Schizophrenia Research Center).

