7: Study Day 3	RBANS	fMRI resting state	BPRS; SANS; GAF; AIMS; C-SSRS	fMRI sensory + cognition; anatomical MRI; food- related questionnaires (TFEQ; FCQ; PFS; VAS); weight; subjective improvement; CO breath test; COVID-19 impact; Post MRI questionnaire	Pill log, pill Count	Side effects; physical exam; MRI screening form; concomitant meds; vital signs; urinalysis

Possible Adverse Events

The investigators will record side effects weekly. Subjects will be asked each week to report dizziness, headache, nausea, hallucinations, paranoia, anxiety, depression, palpitations, urinary urgency, flatulence, peripheral sensations, and abdominal pain and other symptoms, as specified in the side effects questionnaire. If an adverse side effect deemed to be related to the drug is severe enough to require medical treatment, then the subject will be withdrawn. Their adverse side effects will be followed up with repeat medical and laboratory examinations, as clinically indicated, until the adverse side effect is resolved. A subject may voluntarily withdraw because of discomfort unrelated to the drug, such as dislike of the experimental protocol; these subjects will be replaced.

Safety issues that would lead to stopping the experiment are treatment-emergent vital signs in a medically compromised range (see subject stopping criteria) in any subject or drug-related side effects rated above moderate in two or more individuals.

Stopping criteria are as follows: An individual will be withdrawn by the investigator if there is a serious adverse event, including but not limited to severe weight loss, prolonged (more than a few days) insomnia, passing out, and severe agitation/hostility. Doses will not be administered in subsequent studies if they are found to produce an increase or decrease in pulse rate of 30% or above 110 beats per minute or an increase or decrease in blood pressure above 200/110 or below 90/60 mmHg. No rescue medications will be used.

D. Description, Risks and Justification of Procedures and Data Collection Tools:

Symptom Measures/Questionnaires

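### The exploratory symptom scales from a two-period crossover are compared by paired t-tests with no period term, and the C-SSRS is t-tested with no score defined

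*Combined protocol and SAP*

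**What the plan says.** Section IV.C describes a double-blind crossover: about 4 weeks on levetiracetam (LEV), about 4 weeks on placebo, and a washout of about 4 weeks between them. On allocation it says only: "A statistician involved in the study will determine the treatment randomization scheme". No ratio or blocking is given.

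Section IV.F assigns methods by outcome:
- RBANS: "Comparisons (LEV vs. placebo) will be performed using mixed-effects, repeated measures models".
- fMRI: "Condition effects (LEV vs. placebo) will be analyzed using mixed-effects, repeated measures models".
- Clinical symptoms: "Effects of drug on BPRS, C-SSRS, SANS, GAF, and AIMS scores in patients will be evaluated using two-tailed paired t-tests". Total scores are judged at p < 0.05 and subscales at a corrected threshold.

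The clinical text does not say whether the paired values are raw end-of-period scores or changes from each period's pre-dose score.

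Endpoint 4 in section IV.A is headed exploratory and names BPRS, SANS, GAF and AIMS. The C-SSRS is not in it. Section IV.D says that the C-SSRS serves to assess suicidal ideation and comes in two versions, but defines no total, category or event. Under Treatment Arms 1 and 2 and the Study Days, it is given three times on treatment in each period: by phone within about 1 week, at the check-in at about week 2, and on the Study Day at about week 4.

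The AIMS depends on available time under Screening Visit, and on time and the study physician's recommendation under Baseline Study Day. Later Study Days repeat the Baseline measures. The table of study procedures lists the AIMS without condition at Screening and on all four Study Days.

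**The concern.** There are three separate weaknesses.

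1. **Period.** Any general change between the first and second treatment period enters the within-person difference with opposite sign in the two sequences. A paired t-test counts that as noise. If the sequences are unequal among those analysed, part of the shift also enters the estimate.
2. **Complete pairs.** Anyone without a score in both periods drops out of the test. That can include participants whose drug-related side effect is "severe enough to require medical treatment, then the subject will be withdrawn". Of voluntary withdrawals unrelated to the drug, the plan says "these subjects will be replaced", without naming the sequence that a replacement joins.
3. **Undefined or selected scores.** Someone will have to choose a C-SSRS score after the fact. If the AIMS is done only when time or the physician allows, its pairs are a selected subset.

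At stake are the efficiency and meaning of the exploratory symptom comparisons, and a suicidality p-value that nobody could reproduce from the plan.

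**Working it through.** The documents give no sample size, SD, effect, dropout rate or allocation ratio, so there is no stated figure to reproduce. N, effects, shifts and event counts below are assumptions. SD means the SD of the within-person LEV-minus-placebo difference, set to 1.

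**Period shift.** Let τ be the treatment effect and π the period-2-minus-period-1 shift. The difference D has mean τ − π for LEV first (n_LP people) and τ + π for placebo first (n_PL people). The paired estimate therefore has expectation τ + π(n_PL − n_LP)/N.

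*Balanced sequences.* The second term is zero, so there is no bias. The paired test, however, estimates a variance of about 1 + π² instead of 1. At π = 0.5 the SE is overstated by √1.25 = 1.118, and at π = 0.25 by √1.0625 = 1.031. Power at τ = 0.5, with the paired test simulated and the period-adjusted test from the noncentral t (N − 2 df, noncentrality 0.5√N):

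| N | Paired, π = 0.25 | Paired, π = 0.5 | Period-adjusted |
|---|---|---|---|
| 20 | 0.54 | 0.47 | 0.56 |
| 30 | 0.73 | 0.67 | 0.75 |
| 40 | 0.86 | 0.81 | 0.87 |

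The paired test's type I error at π = 0.5 is about 0.03 at each N. With no shift the two methods agree.

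*Unequal completers (LEV first : placebo first = 8:12, 12:18 or 16:24), π = 0.5.* Bias = 0.5 × (12 − 8)/20 = 0.10 SD, and the same for the other two. Type I error is about 0.045, 0.05 and 0.06. Under simple 1:1 allocation a split this uneven or worse has probability 0.50, 0.36 and 0.27. Averaged over such allocations the error is zero and the type I error is 0.05.

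**Incomplete pairs.** If 4 of 30 participants miss period 2 at random, keeping them in a mixed model lowers the SE by only about 1–3%. If withdrawal is caused by worsening on LEV, a model without week-2 scores recovers none of the lost shift. Adding week-2 BPRS and keeping the week-4 contrast recovers 0–2% for period-1 withdrawals and 12–21% for period-2 withdrawals, or 20–29% and 34–41% with a participant-by-period effect.

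**C-SSRS.** Suppose it were scored yes/no with n = 30, with a cases positive on LEV only and none on placebo only. The paired t statistic is √(29a/(30 − a)), and the exact McNemar p is 2 × 0.5^a.
- a = 4: t = √(116/26) = 2.11, p = 0.043; McNemar p = 0.125.
- a = 5: t = √(145/25) = 2.41, p = 0.023; McNemar p = 0.063.
- One placebo-only case added: 0.184 against 0.375 (a = 4), and 0.103 against 0.219 (a = 5). Neither test is then significant.

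**A trap in the replacement model.** Suppose pre-dose scores enter as responses, LEV is coded 1 only after LEV treatment, and there is no pre/post term. Let both treatments share a pre-to-post change of 1. Each person's single LEV observation averages 1. The other three (two pre-dose, one placebo post-dose) average 1/3. The apparent LEV effect is 1 − 1/3 = 0.667. With a pre/post visit term it is 0.

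**The case against.** The strongest defence is that a paired t-test is a legitimate crossover analysis. With balanced sequences it errs on the safe side, and it loses noticeable power only if the shift is near 0.5 SD. No document supports a shift that large. Section IV.B also excludes recent antipsychotic changes (under 2 months) and psychiatric hospitalisation (under 3 months), which favours stable ratings. All of this stands, and it limits the size of the point.

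A reader might infer that RBANS and fMRI receive a period adjustment which the symptom scales are denied. The documents do not support that: the mixed models have no listed terms, so the contrast is one of model class only.

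The choice of visits is less open than it may seem. SANS and GAF have one on-treatment assessment per period, on Study Days 1 and 3. Only BPRS and the C-SSRS have earlier on-treatment contacts. The question of raw score or change from pre-dose remains.

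The C-SSRS comparison of tests assumes a yes/no score and no placebo-only case, and the disagreement at p < 0.05 vanishes with one such case. Absence from endpoint 4 also shows little, since endpoint 8 covers side effects and tolerability. What stands is that a t-test is planned on a score that is never defined.

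The AIMS discrepancy may be a table convention. The table also omits the text's conditions on the Baseline physical exam, the CO breath test, the screening blood draw, and check-in weight and vital signs. That makes the discrepancy minor, but the selected-subset caveat still applies if the text governs.

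**Conclusion.** The point holds and is minor. The paired t-tests leave out a period term that costs one degree of freedom. Under the assumed 0.5 SD effect and 0.5 SD shift, this loses 0.06 to 0.09 in power at N = 20 to 40 (0.87 − 0.81 and 0.56 − 0.47). Under a 0.25 SD shift the loss is close to nothing. The C-SSRS test cannot be interpreted as written, whatever the numbers turn out to be.

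Three stronger readings are not supported:
- *The symptom comparisons are biased.* This needs both a period shift and unequal sequences among completers. The documents establish neither; they only fail to rule out the imbalance.
- *Harms go unmonitored.* Side effects are recorded weekly, the C-SSRS is given at several contacts, and the rules for stopping the experiment include "drug-related side effects rated above moderate in two or more individuals". The defect is in the group comparison, not in the surveillance.
- *A mixed model would repair withdrawals caused by the drug.* It would not, or only in small part.

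The primary RBANS analysis is unaffected.

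**What to change.** - **BPRS, SANS and GAF totals.** Analyse the scores at the end of each treatment period (Study Days 1 and 3) with a mixed-effects crossover model: treatment, period, sequence and random participant. Include participants who have only one period. If Baseline and Post-Washout scores enter as responses, always add a pre/post visit term and let treatment act only at post-dose visits. If week-2 BPRS is added, also include treatment by visit and keep the week-4 LEV–placebo contrast as the estimate. State that the model does not correct for informative withdrawal.
- **C-SSRS.** Replace the t-test with counts and a listing of participants with new or worse ideation or behaviour, by treatment and period, from every C-SSRS contact and including those who withdraw.
- **AIMS.** Reconcile the conditional text (Screening Visit, Baseline Study Day) with the unconditional table of study procedures. If it stays conditional, report it as a selected subset. If it is unconditional, use the same crossover model.

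The cost is SAP wording, one degree of freedom for period, and correcting the AIMS text or the table so that they agree. The BPRS, SANS, GAF and C-SSRS analyses use data already scheduled, and no new visits are needed.
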